11.2. Study Candidate Screening

After approval by the investigator's Ethics Committee (EC) and the sponsor or delegated representative, the investigator will follow SOC practices to screen subjects for inclusion in the study.

11.3. Informed Consent

During the Enrolment and Consenting Visit (Section 11.4), a qualified center representative will review the consent with a potential subject. The subject will be encouraged to ask any questions about the study. All questions from the subject should be addressed prior to the subject signing the informed consent. If the subject signs the informed consent, a signed copy should be provided to the subject and the original should be filed in the electronic or paper medical records. Documentation of the consent process by the person obtaining consent should be filed in the subject study file. No study-specific data collection of any procedure should be conducted prior to consent.

11.4. Enrolment and Consenting Visit (Day 0, 0 to 45 days post implant procedure, alternative >90 days post MI)

Prior to initiating any study procedures, the investigator must ensure that appropriate informed consent has been signed and dated (Section 21). Subjects will sign and date the ICF post successful implant or minimum 3 months post MI, PCI, or CABG.

Subjects who meet all of the entry criteria and consent to the evaluation are eligible. The enrolment for this registry will occur up to 45 calendar days after the device system implantation.

Subjects are considered enrolled after they have met all inclusion criteria, none of the exclusion criteria, and provided written informed consent in accordance with applicable regulatory agency and EC requirements.

The data collection at enrolment includes: demographic data, clinical assessment, medical history and co-morbidities, subject information and medical history; subject status and clinical assessment per SOC; and details on previously/currently implanted devices.

Subject information and medical history

- **Demographic data:** age at time of consent; gender.
- **Clinical assessment:** weight, height, BMI, blood pressure, NYHA Class.
- **Medical history / co-morbidities:**
 - **Subject etiology:** ischemic cardiomyopathy; idiopathic cardiomyopathy; valvular cardiomyopathy; hypertrophic cardiomyopathy; congenital heart disease; infiltrative disease; neuromuscular disease (including myotonic dystrophy and Kearns-Sayre syndrome).

- **Associated diseases/risk factors:** previous MI; previous hospitalization for HF; hypertension; diabetes type I and II; renal disease (BUN); chronic pulmonary disease; smoking in the last 5 years, peripheral artery disease; other known malignancies (tumor, lymphoma or leukemia); other chronic diseases.
- **Additional rhythm disease:** information will be collected on additional relevant rhythm diseases: AV block; sinus node dysfunction; paroxysmal, chronic, persistent atrial fibrillation; chronotropic incompetence.
- **Other subject history:** previous stroke; shock; previous ablation (AV node, atrial fibrillation or atrial flutter).
- **LVEF:** measured or estimated within the last 12 months and documented in the subject's medical file: fully preserved ($\geq 50\%$); partially preserved (40%-49%); reduced (<40%).
- **QRS:** intrinsic
- **Current/concomitant cardiac medication:** documentation of the following current/concomitant medication classes being administered: Angiotensin Converting Enzyme (ACE)-inhibitor/Angiotensin II (ATII) receptor antagonist; antiarrhythmic; anticoagulant; antiplatelet; Aldosterone-antagonist; beta-blocker; Digitalis; diuretics; statins; calcium antagonists.

Documentation of implanted devices

- **ICD, CRT-D, PM/CRT-P, etc. data:** Implant date, number of days implanted, model, serial number
- **Pacing lead data:** cardiac chamber (atrial and ventricular), number of days implanted and lead model (serial number) and manufacturer

Some subjects received a device system for the first time whereas others received a replacement procedure of existing systems (usually pulse generator due to battery depletion but may also include lead extractions due to lead failure or other reasons for system component replacement). Data (implant date, number of years implanted, model and manufacturer) for previous device systems will also be collected.

Defibrillator therapy for all ICD and CRT-D devices in the protocol must be programmed according to the specifications provided in Table 11.4-1, Table 11.4-2 and Table 11.4-3, respectively.

Any deviation from protocol requirements for medical reasons will need to be documented as an adverse event and as a deviation from the protocol. The programming is considered non-invasive; specifications are provided to ensure that the devices are operated per BSC IFU. Any programming not per the specifications below will be considered a CIP violation.

Table 11.4-1: Programming Requirements for High Rate Cutoff

Parameters	Programming
Ventricular Tachy Therapy Zones	2 and one optional high rate zone
Zone 1 (VT) Rate Cutoff	170 bpm
Zone 1 (VT) Zone Rate Therapy	Monitor Only (No Therapy)
Zone 2 (VF) Zone Rate Cutoff	200 bpm
Zone 2 (VF) Zone Duration	2.5 seconds or longer
Zone 2 (VF) Zone Therapy	Defibrillator therapy (ATP (optional) + Shock)
Zone 3 (VF)	>200 bpm Optional programming for all parameters

Table 11.4-2: Programming Requirements for Long Delay

Parameters	Programming
Ventricular Tachy Therapy Zones	3
Zone 1 (VT-1) Zone Rate Cutoff	170 bpm
Zone 1 (VT-1) Zone Duration	60 seconds
Rhythm Detection Enhancements (Rhythm ID):	ON; Program Passive and Active Methods ON with Fallback LRL
AF Threshold	170 bpm
Stability	20 ms
Post-Shock Detection:	ON
SRD	OFF
Zone 1 (VT-1) Zone Therapy	Defibrillator therapy (ATP (optional) + Shock)
Redetection Duration	Nominal

Zone 2 (VT) Zone Rate Cutoff	200 bpm
Zone 2 (VT) Zone Duration	12 seconds
Rhythm Detection Enhancements (Rhythm ID):	ON, Same as VT-1 Zone
Zone 2 (VT) Zone Therapy	Defibrillator therapy (Shock + ATP (Optional))
Redetection Duration	Nominal

Zone 3 (VF) Zone Rate Cutoff	250 bpm
------------------------------	---------

Table 11.4-2: Programming Requirements for Long Delay

Parameters	Programming
Zone 3 (VF) Zone Duration	2.5 seconds
Zone 3 (VF) Zone Therapy	Defibrillator therapy (ATP (optional) or Shock)

Other parameters may be programmed following physician's discretion

Table 11.4-3: ICD Programming Option 3 (if applicable for a specific device)

Conditional Shock Zone	200 bpm
Shock Zone	250 bpm

Baseline subject status and clinical assessment data collection from if performed as standard of care

All uploaded data must be anonymous and de-identified to assure data confidentiality

- **12-lead ECG recording pre and post implant and at close-out (data collection and document upload in e.g. pdf format) as SOC:** date (pre-implant maximum 45 days before implant; latest available maximum 12 months prior to enrollment for non-device cohort); rhythm (normal sinus rhythm, junctional rhythm, atrial fibrillation, paced); resting heart rate; intrinsic or paced QRS width; PR interval, QT interval; QRS morphology (normal, right bundle branch block, LBBB, other conduction disorders).
- **Echocardiography or equivalent method as SOC:** will be used to determine basic measures: LVEF, diastolic diameters, volumes (Implant criteria and therapy efficacy data).
 - Device cohorts: data obtained within the last 3 months prior to enrolment are to be provided
 - Non-device cohort: latest data obtained within the last 12 months prior to enrollment in case there was no documented HF decompensation, MI or revascularization, otherwise within the last 3 months prior to enrollment are to be provided
- **MRI scan:** data on actual number of MRI scans performed according to center's SOC since the implant procedure, including information about scanned body parts, will be collected.
- **Physician's judgment:** judgment on therapy status / outcome / CRT therapy delivery (success yes/no) / defibrillator therapy (ATP/Shock delivered: yes/no).
- **Biomarkers for heart failure:** parameters as routinely evaluated prior to device implant or as part of standard visit for non-device subjects will be documented by the

site teams in the eCRF including name of parameter, date of analysis, result, and normal range according to local lab.

Collected standard biomarkers are: amino-terminal pro-peptide B-type natriuretic peptide (NT-proBNP), BNP, Troponin T, Troponin I, creatinine, BUN, and estimated glomerular filtration rate (eGFR)

Optional additional biomarkers collected from SOC diagnostics are: CK-MB, C-reactive protein, TNF-alpha, galectin-3 (Gal-3), parathyroid hormone (pTH), CA125, ST2

However, the identification of laboratory parameters as biomarkers for heart failure is left to the discretion of each individual investigator.

Risk factor assessment

The following risk marker will need to be assessed (at all FU scheduled and unscheduled):

1. Myocardial infarction status
2. Last available EF status (value/ date)
3. Atrial fibrillation
4. Smoking
5. QRS morphology and width
6. Renal function
7. Diabetes type I and II
8. NYHA assessment
9. Age of subject

- Therapy judgment: appropriate, inappropriate, both, unclear
- CRT only: V-V timing of programmed vector
- MRI scan done during last 6 months observational period: yes/no
- Reason for MRI scan documented as related to diagnostics or related to a known SAE
- After any MRI, appropriate pacing and sensing need to be verified and documented as an unscheduled visit. In case of an increased pacing threshold or inappropriate sensing or any other device abnormality, an event report must be completed.

Latitude

All Latitude alerts related to ventricular episodes and heart failure (if applicable) must be programmed on. All other alerts can be programmed on the physician's discretion or following hospital routine. If Latitude is available for a device, the device should be programmed ensuring that a Latitude report is created bi-weekly or at a higher frequency so that Latitude reports can be collected timely to corresponding clinical events.

Subjects will have their device performance and diagnostic data downloaded remotely into the Latitude database. The Latitude BSC team will collect device reports in the following cases:

- After all ventricular treatment Latitude alerts
- After all heart failure related Latitude alerts (if available)
- After the center reported serious adverse (device) events if these were related to ventricular episodes or heart failure events
- After the center reported SADE or ADE, including all inappropriate device treatments

The collected and anonymized Latitude reports will be uploaded into the study database for analysis.

If for any reason patients cannot be connected to Latitude, endpoint related data can be uploaded into the database by the site (e.g. electrogram (EGM) for ventricular arrhythmias).

11.5. Six-monthly Visit

Subjects will be visited every 6 months from enrolment (Day 0) until Close-out Visit. During the 6-monthly follow-up visit, device assessment/interrogation should be performed according to SOC practices. Details on the occurrence of any adverse device effects (ADEs), SAEs, SADEs, and device deficiency (DD), which have occurred since enrolment (Day 0), are to be recorded.

Echocardiography or equivalent method according to center's SOC will be used to determine basic measures: LVEF, diastolic diameters, and volumes. If the echo is not done per SOC, no deviation will be recorded.

Data on actual number of MRI scans performed according to center's SOC since the enrolment, including information about scanned body parts, reason for scan, etc., will be collected.

Subjects will have their device performance, all Latitude alerts on. Latitude report is requested every 14 days, and diagnostic data are downloaded remotely by the Latitude BSC team as Latitude report during this visit timeframe.

Latitude remote device interrogation is requested to be programmed every 2 weeks or more frequent.

Subjects that receive re-implant, repositioning, device upgrade or new device implant post enrolment, as determined by the investigator, will continue to follow same initial procedures and schedules as described for Day 0 at the initial enrolment. The reason for re-implant/revision is to be documented as an Adverse Event in the eCRF.

Physician's judgment on therapy and risk factor assessment will be collected on standard follow-up CRF as planned at enrolment. In addition to the Re-implant CRF, the form for unscheduled visits will be used for event reporting.

If there were any protocol deviations since the last study visit, they have to be recorded.

11.6. Re-implant, Device System Revision, Device Upgrades, or New Device Implant post Enrolment

The Re-implant or New Device Implant post Enrolment visit is optional and needs to be performed only if re-implant (invasive procedure towards the evaluated therapy system), device system revision, device upgrade, or new device implant occurs while subjects are in the study.

Subjects that receive re-implant or new device implant post enrolment, as determined by the investigator, will undergo the same procedures as described for Day 0. The reason for re-implant/revision is to be documented in the eCRF.

Details on the occurrence of any adverse device effects (ADEs), SAEs, SADEs, and DD are to be recorded.

If there were any protocol deviations since the last study visit, they have to be recorded.

11.7. Interim or Unscheduled Visit and Event Report (SAE/SADE related clinical care visit)

The Interim Visit is optional and should be performed according to the SOC at the center. This visit can be completed in person at the clinic or over the phone at any time other than study scheduled visits.

All clinic visits that occur outside the specified protocol visit window will be classified as "Unscheduled CIP Visits". Unscheduled visits triggered by a specific event (e.g. adverse event, Latitude alert, patient request etc.) and not by standard routine control (e.g. device check-up standard by the institution, wound check, standard echo or ECG, blood analysis etc.) must be documented.

During this follow-up visit, details on the occurrence of any SAEs, SADEs, and DDs, which have occurred since the last visit, are to be recorded.

Events which already have been reported as part of an unscheduled visit do not need to be reported again during a CIP defined visit.

Data on actual number of MRI scans performed according to center's SOC since the last visit, including information about scanned body parts, will be collected.

Subjects will have their device performance, nominal alerts, and diagnostic data downloaded remotely from the Latitude BSC team during this visit. Risk factor assessment will be collected.

It is possible that more than one Interim Visit may occur if the SOC at the center requires more than one visit throughout the visit window. Any additional Interim Visits should be conducted similarly.

If there were any protocol deviations since the last study visit, they have to be recorded.

11.8. Close-out Visit

All subjects will remain in the study until the last subject completes his/her last visit. The maximum study duration for any subject will be 34 months (FSFV to LSLV). For the last subject enrolled, the study duration is 12 months.

As soon as the last subject was enrolled, planning of Close-out Visits for all subjects starts.

All close out visits will be documented on a specific Close out CRF. The time window for the Close-out Visits of all subjects starts 2 months before the last subject enrolled has completed 12 months and ends 4 months after the last subject enrolled has completed 12 months.

In case the time window for the Close-out Visits does not follow SOC, for HF subjects in a hospital, any follow-up appointment after 6 months which is closest to the study window might be defined as Close-out Visit.

During the Close-out Clinic Visit, a clinical assessment/physical exam should be performed in order to document the health status of the subject in addition to any ADEs, SA(D)Es, and DDs that may have occurred since the last visit. The physician's judgment on therapy outcome will be recorded. Current medication classes prescribed as well as a device assessment/interrogation should also be performed according to SOC practices.

The duration of QRS, intrinsic or paced, will be collected.

Full ECG recording is required at this visit if it is SOC of the center and data should be uploaded to the study database.

If Echocardiography or equivalent method is SOC of the center, it will be used to determine basic measures: LVEF, diastolic diameters, volumes.

Data on actual number of MRI scans performed according to site's SOC since the last visit, including information about scanned body parts, will be collected.

Subjects will have their device performance, nominal alerts and diagnostic data downloaded remotely from the Latitude BSC team during this visit timeframe.

Available results for heart failure related and other SOC biomarkers that were generated within the last 4 months prior each subject's individual close-out visit will be documented in the eCRF including name of parameter, date of analysis, result, and normal range according to local lab.

Once the subject completes the Close-out Clinic Visit, participation in this registry study has been completed. In case of premature termination of the study, data collection will stop accordingly. As this is an observational study, subjects will be managed according to center SOC following termination/completion of the study.

If a device-related event (unanticipated SADE [USADE], SADE, ADE) is ongoing at the time of study completion, the subject may be asked to remain enrolled in the study and provide additional information regarding the event until the event is resolved. The physician will provide treatment for any ongoing events according to SOC regardless of whether the subject agrees to continue participating in the study.

Physician's judgment on therapy and risk factor assessment will be done. Device therapy will be documented on an event form as well as all device deficiencies including false positive Latitude Alerts.

If there were any protocol deviations since the last study visit, they have to be recorded.

11.9. *Source Documents*

Table 11.9-1 summarizes all source data requirements for this CIP. Most source documents will be filed in the subject's hospital chart since all procedures will follow SOC. All source documents should be filed in the subject hospital chart since all procedures will follow SOC. Some source documents (ECG strips, Echo imaging, and Latitude recordings) may be stored electronically on a secured study database.

Only a copy of the subject consent will be kept in the administrative study binder and no subject study binder will be generated.

All personal information should be removed from all documents prior uploading into the study database and replaced by the study ID. In case this is not possible the database administrator will anonymize data as required.

Table 11.9-1: Source Documentation Requirements

Requirement	Disposition
Subject Consent Form	1-Retain subject file, 2 administrative study binder, 3-Subject copy
Enrolment and Baseline Data	Retain in subject hospital file
Implant Measurement	Retain in subject hospital file
Implant Procedure Medical Records	Retain in subject hospital file,
6-monthly Clinic Visit Data	Retain in subject hospital file
Interim /Unscheduled CIP Visit Data	Retain in subject hospital file
Close-out Clinic Visit Data	Retain in subject hospital file
Adverse Events and Device Event Data	Retain in subject hospital file
CIP Deviation	Report in Study Database
Study Withdrawal Data	Retain in subject hospital file
ECG e-Recording	Retain in subject hospital file and copy upload to study database
Echocardiographic Imaging e-Recording	Retain in subject hospital file
Device Interrogation Printouts	Retain in subject hospital file
MRI pictures, videos, and reports	Retain in subject hospital file
Latitude device and alert data	Retain in subject hospital file Latitude database and copy of the Latitude report upload into study database

Abbreviations: CIP = Clinical Investigation Plan; ECG = electrocardiogram; MRI = magnetic resonance imaging

12. Statistical Considerations

12.1. *Endpoints*

12.1.1. Primary Endpoint for ICD Treated Subjects

The primary endpoint for ICD treated subjects is:

- Composite rate of first appropriately treated ventricular arrhythmia (by ATP or shock) or life-threatening symptoms associated to ventricular arrhythmia (defined as hemodynamic instability which requires treatment), whichever comes first under MADIT Arm B or C programming conditions in a study population with a majority of Japanese subjects

Based on the MADIT RIT study⁴, we estimate that 5% of the ICD treated subjects will present an appropriately treated first ventricular arrhythmia associated symptom (by ATP or shock) within one year.

12.1.1.1. Hypotheses

The null and alternative hypotheses are as follows:

H_0 : The ventricular arrhythmia associated symptoms free-rate from 0-12 months $\leq 85.0\%$

H_A : The ventricular arrhythmia associated symptoms free-rate from 0-12 months $> 85.0\%$

The null hypothesis (H_0) will be rejected if the lower one-sided 97.5% confidence bound for the ventricular arrhythmia associated symptoms free-rate is greater than the performance goal of 85.0%.

12.1.1.2. Statistical Methods

When the final study subject reaches the final CIP required follow-up visit, the primary analysis will be performed based on the Kaplan-Meier method for the estimation of the 12-month ventricular arrhythmia associated symptoms free-rate, including the lower 97.5% confidence bound (computed based on log-log methodology). This Kaplan-Meier analysis will begin at the time of implant. Subjects that withdraw consent or are lost-to-follow-up prior to the 12-month endpoint evaluation will be censored at their date of last contact. All subjects actively enrolled will be included in the endpoint analysis.

The null hypothesis will be rejected and the endpoint considered met if the lower 97.5% confidence bound for the ventricular arrhythmia associated symptoms free-rate at 12 months is greater than 85.0%.

Additionally, a Kaplan-Meier survival time-to-event curve along follow-up will be provided.

The primary analysis above will be performed for CRT-D and ICD cohorts combined as well as for ICD treated subjects separately.

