Statistical Test Method (continued)	
 • The primary endpoints above will be performed for ICD and CRT-D cohorts combined (primary analysis) as well as for ICD and CRT-D treated subjects separately (for descriptive purpose). • For PM/CRT-P treated subjects, the all-cause mortality free-rate (survival rate) from implant will be calculated as the proportion of actively enrolled subjects who are alive 12 months after implant. The null hypothesis will be rejected and the endpoint considered met if the lower one-sided 97.5% confidence bound for the proportion of subjects with no death is greater than 80.0%. • For Non-device subjects (ESC Guideline 2016 Indicated but not implanted), the all-cause mortality free-rate (survival rate) from enrolment will be calculated as the proportion of actively enrolled subjects who are alive 12 months after enrolment. The null hypothesis will be rejected and the endpoint considered met if the lower one-sided 97.5% confidence bound for the proportion of subjects with no death is greater than 80.0%. • Exploratory analyses for ICD and CRT-D Cohorts combined versus Non-Device Cohort (ESC Guideline 2016 Indicated but not implanted): propensity score matching comparison of all-cause mortality rate and composite rate of HF events between pooled cohorts with device (ICD and CRT-D) versus the Non-Device Cohort regarding 7 risk factors at baseline (NYHA Class III or IV, renal dysfunction [chronically BUN >26 mg/dL / ≥ 9.28 mmol/L], diabetes type I and II, chronic atrial fibrillation [permanent or persisting according to ESC Guideline 2016], prior MI, age >70 years, smoking today or during last 5 years). 
Further details on analytical methods can be found in Section 12 of the CIP

Sample Size Parameters	
ICD Treated Subjects:
 
The minimum required sample size to statistically power the ventricular arrhythmia associated symptoms free-rate through 12 months post implant is 117 subjects. Sample size was calculated assuming a 95.0% ventricular arrhythmia associated symptoms free-rate, a performance goal of 85.0%, one-sided alpha level of 0.025, 90% power, and 20% attrition.

Heart Failure Indication and Sudden Cardiac Death Prevention Trial Japan
Hinode

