12.1.2.2. Statistical Methods

When the final study subject reaches the final CIP required follow-up visit, the primary analysis will be performed based on the Kaplan-Meier method for the estimation of the 12-month ventricular arrhythmia associated symptoms free-rate, including the lower 97.5% confidence bound (computed based on log-log methodology). This Kaplan-Meier analysis will begin at the time of implant. Subjects that withdraw consent or are lost-to-follow-up prior to the 12-month endpoint evaluation will be censored at their date of last contact. All subjects actively enrolled will be included in the endpoint analysis.

The null hypothesis will be rejected and the endpoint considered met if the lower 97.5% confidence bound for the ventricular arrhythmia associated symptoms free-rate at 12-months is greater than 87.0%.

Additionally, a Kaplan-Meier survival time-to-event curve along follow-up will be provided.

The primary analysis above will be performed for CRT-D and ICD cohorts combined as well as for CRT-D treated subjects separately.

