In case of shock or ATP treatment is noted by the subject or site, an SAE should be documented (life-threatening arrhythmia and corrective action is ATP or shock). Several shocks or ATP treatments on the same day are to be reported as one SAE. The event will be recorded as related to an arrhythmia. All events of shock will be captured by the Latitude system. If an event of shock is captured by the Latitude system, but has not been documented as an AE, the site will be asked to provide the documentation.

Any ATP treatment or shock that was inappropriate is to be documented as device deficiency. Multiple inappropriate ATP treatments or shocks on one day can be summarized in one device deficiency report.

Refer to the BSC Physician's Lead Manual for the known risks associated with the study devices.

All device-related AEs will be evaluated at least monthly during the trial and might be extracted from the database in order to pool those data with other available data sets (e.g. trials). Pooling of those datasets on product performance on a broader sample size will be done especially to support safety aspects of all medical devices in this trial.

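### For the ICD/CRT-D arrhythmia endpoint, event-free subjects should be censored at the last device read-out rather than at last contact; the bias runs toward success but matters only for subjects without read-outs

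*Combined protocol and SAP*

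**What the plan says.** Section 12.1.1.2 estimates the 12-month event-free rate for ICD subjects by Kaplan-Meier from implant and compares the log-log lower 97.5% bound with 85.0%. On incomplete follow-up it says: "Subjects that withdraw consent or are lost-to-follow-up prior to the 12-month endpoint evaluation will be censored at their date of last contact". Section 12.1.2.2 treats CRT-D subjects (goal 87.0%) the same way: they "will be censored at their date of last contact". Sections 12.1.3.2 and 12.1.4.2 use the same sentence for mortality. Last contact is not defined.

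The endpoint (Sections 12.1.1 and 12.1.2) is a first ventricular arrhythmia appropriately treated by ATP or shock, or hemodynamic instability from ventricular arrhythmia that needs treatment.

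Device information reaches the study as follows:

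- **Clinic visits (Section 11.5):** "device assessment/interrogation should be performed according to SOC practices". Table 11.1-1 also marks interrogation as standard of care.
- **Interim visits (Section 11.7):** "This visit can be completed in person at the clinic or over the phone at any time other than study scheduled visits". The same section foresees a remote Latitude download at that time.
- **Remote monitoring (Sections 11.4 and 11.5):** two-weekly interrogation is requested and ventricular alerts must be on. Table 11.1-1 marks Latitude data as required at every visit type.
- **Unconnected subjects (Section 11.4, Latitude):** "If for any reason patients cannot be connected to Latitude, endpoint related data can be uploaded into the database by the site". Sections 5 and 8 ask for a deviation report; neither removes the subject from the study.
- **Coverage (Section 20.2):** "All events of shock will be captured by the Latitude system". There is no matching statement for ATP.
- **Loss to follow-up (Section 10.2):** established by phone calls and a letter, with no final read-out.

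**The concern.** For mortality the rule is sound, because any contact proves the subject was alive. For a device-recorded event it is not: a phone call cannot rule out an ATP-treated arrhythmia that the subject did not feel. A subject censored at last contact then stays in the risk set for a period in which a silent event could not have been seen.

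The plan also does not say how to treat a subject who stays in the study without a read-out. By default that subject is carried event-free to 12 months. Both omissions lower the apparent event rate and make the 85% and 87% goals easier to meet.

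**Working it through.** **1. The plan's own figures.** The Synopsis assumes a 95.0% event-free rate for ICD, with "a performance goal of 85.0%, one-sided alpha level of 0.025, 90% power, and 20% attrition". For CRT-D it assumes 97.0% against 87.0%, with the same alpha, power and attrition. The smallest exact-binomial samples are:

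- ICD: n = 93, success at 86 or more event-free, exact alpha 0.0235, power 90.6%; 93/0.8 = 116.25, so 117.
- CRT-D: n = 76, success at 72 or more, exact alpha 0.0241, power 92.2%; 76/0.8 = 95.

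Both match Table 12.1-1. The sample sizes are not in question.

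**2. Lost subjects who transmit every 14 days.** Take the true ICD rate at the goal.

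- Annual event hazard: −ln 0.85 = 0.1625.
- Annual loss hazard at 20% attrition: −ln 0.80 = 0.2231.
- Gap: 14/365 = 0.0384 year.
- Share of the risk set in an unread last fortnight: about 1 − exp(−0.2231 × 0.0384) = 0.0085.
- Visible cumulative hazard: 0.1625 × (1 − 0.0085) = 0.1611. The expected estimate is exp(−0.1611) = 85.1%, a shift of about 0.1 point.

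Simulation agrees (10,000 runs, n = 117, constant hazards, log-log bound). It gives 85.1% and false success of 1.9%, against 85.0% and 1.7% with no gap. False success is the chance that the bound clears the goal when the true rate equals the goal.

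**3. Longer gaps, in lost subjects only (assumed).**

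| Gap between last read-out and last contact | Estimate | False success |
|---|---|---|
| 2 months, all lost subjects | 85.4% | 2.2% |
| 6 months, 10–25% of lost subjects | 85.2–85.3% | 1.6–1.7% |
| 6 months, all lost subjects | 86.2% | 3.5% |
| No read-out in any lost subject | 86.5% | 4.1% |

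Through lost subjects alone, the nominal 2.5% is passed only if nearly all of them have gaps of about 6 months or more.

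**4. Subjects with no read-out, lost or retained.** Let u be their share, and assume that no event in them is seen. The expected estimate is u × 1 + (1 − u) × 0.85 = 0.85 + 0.15u. The simulation (6,000 runs) adds a gap of at most 14 days in the other lost subjects.

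| ICD subjects with no read-out (assumed) | Formula | Simulated estimate | False success |
|---|---|---|---|
| 5% | 85.75% | about 85.8% | about 3% |
| 10% | 86.5% | about 86.5% | 3.5–4% |
| 20% | 88.0% | about 88.1% | about 9.5% |
| Any of these, censored at last read-out | – | about 85.0% | 1.3–1.6% |

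The Monte Carlo standard error at 3% is √(0.03 × 0.97/6000) = 0.2 point, so the 5% row lies only just above 2.5%.

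For CRT-D (n = 95) the formula is 0.87 + 0.13u, giving 88.3% at u = 10% and 89.6% at u = 20%. Simulated false success is 2.7% and 5.5%, against 1.1–1.2% with read-out censoring.

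**5. At the planned ICD rate of 95%.** The shift is 0.05u: 0.5 point at u = 10% and 1.0 point at u = 20%, against a 10-point margin.

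**The case against.** The protocol has real controls. Two-weekly interrogation is requested, ventricular alerts must be on, and intended Latitude follow-up is an inclusion criterion. Section 20.1 has the Latitude database checked for unreported arrhythmias at least yearly, and Section 11.7 pairs an interim contact with a remote download. For connected subjects this disposes of the concern, as step 2 shows.

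The large error rates in step 4 come from an assumed share of subjects with no read-out. Most of these would be retained subjects, whom the censoring sentence does not govern. That is also correct: they are exposed by the plan's silence on unread follow-up, and the same change of censoring date repairs both.

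Three stronger readings are tempting and not supported:

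- A reader might infer that gaps of up to 6 months are usual in lost subjects. Adding 10% or 20% unread subjects would then give false success near 5.7% or 12%. Gaps of that length contradict the two-week schedule.
- A reader might infer that nothing is known about a subject after the last read-out. The hemodynamic part of the composite can be reported clinically, and Section 20.2 makes any shock or ATP noticed by subject or site a serious adverse event. Only freedom from the full composite needs the read-out.
- A reader might infer that the rule also discards much observed time in subjects who still transmit after contact is lost. Section 10.2 bars data collection after withdrawal and treats loss to follow-up as leading to it, so little is affected.

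**Conclusion.** The censoring date does not suit a device-recorded endpoint and should be changed, but the flaw does not undermine the design. The direction is toward success. The size is about 0.1 point where Latitude works as requested, and material only if perhaps 5% or more of a cohort has no read-out.

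The step 4 figures are at the upper end. They assume that every event in unread time is missed, whereas symptomatic events may be reported and a later interrogation may recover stored episodes. The documents give neither the gap nor the unread share. Constant hazards and loss unrelated to arrhythmia risk are further assumptions.

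The figures apply to the separate cohorts. The Synopsis makes the combined ICD and CRT-D analysis primary but states no single goal for it, so no combined error rate is given here. The direction would be the same.

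**What to change.** In Sections 12.1.1.2 and 12.1.2.2, and for the combined analysis:

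1. Count every endpoint event observed while consent is in force, whether from the device or reported by the site, at its event date. An event after the last read-out must not be lost to the new censoring date.
2. Censor every ICD or CRT-D subject without an event at the last device interrogation or Latitude transmission, at most 12 months, whether or not the subject was lost.
3. Make upload of episode or electrogram data mandatory for any interrogation done in a subject not on Latitude.
4. Report how many subjects had no read-out, and give the last-contact analysis as a sensitivity analysis.
5. Keep last contact for the mortality endpoints.

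The cost is wording, use of transmission and interrogation dates, slightly less follow-up and a slightly wider bound. The loss grows with the unread share: at 20%, about 23 of 117 ICD subjects (0.20 × 117 = 23.4) would contribute no event-free time. Counting late site-reported events without the matching event-free time leans slightly against success. The last-contact sensitivity analysis leans the other way, so the two together show how much unread time matters.
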